Trial registration:	Swiss Federal Complementary Database Clinicaltrials.gov
Study category and Rationale	Clinical Phase with IMP Category C
Clinical Phase:	Clinical Phase III
Background and Rationale:	About 10% teenagers report moderate to marked depressive symptoms and between 1-6% will develop a paediatric major depressive disorder (pMDD) until adulthood. However, evidence-based treatment approaches are sparse, and the use of SSRIs is heavily debated due to reports of an increase in suicidal ideation and limited efficacy in this age group. Growing evidence suggests that omega-3 fatty acids may be a beneficial treatment in adult MDD (aMDD) with no published study in teenagers, despite of its face validity as a valuable first-line treatment. Meta-analyses of published randomized controlled trials (RCTs) in aMDD show moderate effect sizes, if the proportion of eicosapentaenoic acid (EPA) is >60% of the total omega-3 fatty acids. One small RCT in prepubertal children shows an even larger effect size in favour of omega-3 fatty acids. Higher inflammatory mediators (e.g. c-reactive protein, interleukins and others) have been reported in aMDD and pMDD. Preliminary data suggests that a pro-inflammatory state may serve as predictor for omega-3 fatty acids response. Furthermore, low levels of omega-3 fatty acids have been found in aMDD and pMDD potentially also serving as EPA-response predictors. As MDD is a heterogeneous disease entity, such response predictors should be incorporated into MDD RCTs.

Objective(s):	1) To investigate the therapeutic efficacy and safety of omega-3 fatty acids rich in EPA in pMDD, 2) to demonstrate clinical meaningful effects of omega-3 fatty acid treatment, 3) to investigate inflammatory and bioactive lipid markers as response predictors, and 4) to investigate the relationship between psychopathology (in particular suicidal ideation), illness course and cognition in relation to inflammatory and bioactive lipid markers. 5.) To establish a tissue repository of phenotypically well characterised children and adolescents with pMDD.
Outcome(s):	The German S3 Guidelines for the treatment of depression in children and youth define the background treatment for all participants. All clinical partners will be trained and monitored accordingly. The primary outcomes are the (continuous) Children's Depression Rating Scale-revised (CDRS-R) total score and the (dichotomous) rates of recovery defined by the absence of pMDD for >4months at 36 weeks, as well as response and remission rates at 12 and 36 weeks. Inflammatory mediators in serum using immunoassays, red blood cell omega-3, 6, 9 and trans fatty acids using gas chromatography (GC) and bioactive lipid mediators (e.g. E-series resolvins) using mass spectrometry (LC-MS/MS) will be measured as potential response predictors. Adverse events/ harm endpoints (in particular suicidality) will be coded using MedDRA. Adherence measurements are pill counts, as well as n-3 EPA/DHA levels across the study. Blood samples will be taken at study entry, week 12 and 36.
Study design:	A Swiss, multicentre, randomised, double-blind, placebo-controlled clinical trial.
Inclusion / Exclusion criteria:	The study aims to randomize a sample of 220 individuals aged 8 - 17 years, who are in- or outpatients of a participating centre and have a present primary diagnosis of major depression disorder with depressive symptoms of at least moderate severity. Participants with pre-existing neurological or medical conditions likely to be responsible for the depressive symptoms or other psychopathological diagnoses are excluded.
Measurements and procedures:	The study design incorporates a 1-2week screening, a 7 -10days placebo lead-in and a 36week double-blind placebo-controlled treatment phase. The severity of the depression and psychosocial functioning will be assessed at baseline and at each study visit (twice in the acute phase and twice in the maintenance phase) using a variety of different questionnaires and rating scales. Cognitive testing and biological markers (blood, urine and saliva) will be sampled at baseline and at 12 and 36 weeks. Adherence to the study will be checked by pill count at each study visit and PUFA level measurements in red blood cell membranes at baseline, 12 and 36 weeks will be performed.

Study Product / Intervention:	In the proposed study we use for the active treatment a daily dose of 500mg EPA/ 250mg DHA in our 8 to <13 year olds, and 1000mg EPA / 500mg DHA in our 13 to <18 years olds (which corresponds with the omega-3 fatty acid doses used in adult MDD RCTs). The drug will be administered for 36 weeks.
Control Intervention (if applicable):	Placebo capsules will contain mostly medium chain triglycerides (MCT) and each capsule will also contain 1.6mg of fish oil to mimic the fishy flavour and taste.
Number of Participants with Rationale:	We aim to randomize 220 participants with at least one follow-up assessment in total, resulting in 110 participants per treatment group. Furthermore, we will recruit up to 20 additional patients to account for the number of patients who started antidepressant within the first 6 weeks of treatment. We performed a sample size calculation based on the effect size of 0.54 found in a previous meta-analysis on the effect of omega-3 fatty acids in aMDD. Sample size calculations were then adjusted for a higher placebo-response rate in minors given our multi-centre study. The analysis resulted in the inclusion of 108 patients per treatment group to achieve 80% or greater power to detect a difference of 20% in response rates between the two treatment groups. Our sample of 220 participants exceeds therefore the projected sample size needed to detect a clinical meaningful difference. A detailed explanation of the sample size calculation can be found under Section 11.2.
Study Duration:	The study duration is projected to be about four years months for patient recruitment and assessment and another year to finish up all the analysis and generate the final study report. We expect that all assessments with patients will be completed by March 2022.
Study Schedule:	First participant in: 01.03.2017 Last participant in: 31.05.2021 Last participant out: 31.03.2022 Database closure: 31.04.2022 Final analysis: 01.09.2022 Study report: 31.12.2022

Investigator(s):	
[name] Department of Child and Adolescent Psychiatry University Hospital of Psychiatry University of Zurich [name] [name] [name] [contact] [contact] Email: [contact]
 
[name] Professor and Medical Director Department of Child and Adolescent Psychiatry University Hospital of Psychiatry University of Zurich [name] [name] [contact] Email: [contact]
 
[name] Research Director Department of Child and Adolescent Psychiatry Research Department Universitäre Psychiatrische Kliniken (UPK) Basel [name] [name] [contact] Email: [contact]
 
All other investigators will be documented in the trial master file.

Study Centre(s):	A total of five Cantons of the German part of Switzerland agreed to participate in the multi-centre Omega-3-pMDD trial. The five Cantons include two academic centres (Zürich ZH, Basel-Stadt BS) as well as the inpatient and outpatient services of Canton St. Gallen (SG), Thurgau (TG) and Basel-Land (BL) encompassing all public child- and adolescent psychiatric services in a catchment area of 2.7 Million habitants (ZH 1446.4M, BS 190.6M, SG 495.8M, TG 263.7, BL 283.2).

Statistical Considerations:	The continuous primary outcome measure is the CDRS-R total score. The related dichotomous outcome measures response and remission will be addressed as secondary endpoints. Data analysis will be performed in the intention-to-treat sample using a (generalized) linear random coefficient regression model. We will use multiple imputations for missing data. Under the assumption of random intercepts and slopes for each patient, the overall and treatment group-specific rate of change for the two treatment groups for the primary outcomes will be examined. A comparison on treatment slopes (linear trends with time) will then be conducted. As antidepressant medication prescription is allowed during the trial but might be related to treatment group, the primary analysis will account for antidepressant prescription by jointly modeling time to this event with the primary outcome.
GCP Statement:	This study will be conducted in compliance with the protocol, the current version of the Declaration of Helsinki, the ICH-GCP as well as all national legal and regulatory requirements.

ABBREVIATIONS

5-HIAA	5-Hydroxindoleacetic Acid
5-HT2	5-Hydroxytryptamine
AA	Arachidonic Acid
ADHD	Attention Deficit Hyperactivity Disorder
AE	Adverse Event
ALA	Alpha-Linolenic Acid
ALAT	Alanine Transaminase
ANT	Amsterdam Neuropsychological Tasks
aMDD	Adult Major Depressive Disorder
APA	American Psychological Association
ASAT	Aspartate Transaminase
ASEC	Antidepressant Side Effect Checklist
ASR	Annual Safety Report
AWMF	Arbeitsgemeinschaft der Wissenschaftlichen Medizinischen Fachgesellschaften
BAI	Beck Anxiety Inventory
BDI	Beck Depression Inventory
BHS	Beck Hopelessness Scale
BL	Basel -Land
BPD	Borderline Personality Disorder
BRIEF	Behaviour Rating Inventory of Executive Function
BS	Basel-Stadt
CA	Competent Authority (e.g. Swissmedic)
CAM	Complementary Alternative Medicine
CBCL	Child Behaviour Checklist
CBT	Cognitive behavioural therapy
CDI-2	Children's Depression Inventory
CD-RISC	Connor-Davidson Resilience Scale

CDRS-R	Children's Depression Rating Scale-revised
CEC	Competent Ethics Committee
CGAS	Children's Global Assessment of Functioning
CGI	Clinical Global Impression rating scale
CGI-I	Clinical Global Impression rating scale-improvement
ClinO	Clinical Trials Ordinance
CRF	Case Report Form
CRH	Corticotropin-releasing Hormone
CSF	Cerebrospinal Fluid
CTC	Clinical Trials Centre
CTQ-SV	Childhood Trauma Questionnaire-Short Version
D2	Dopaminreceptor 2
DHA	Docosahexaenoic acid
DNA	Desoxyribonuclein acid
DM	Data Management
DSM-IV	Diagnostic and Statistical Manual of Mental Disorders-4th edition
EBPI	Epidemiology, Biostatistics and Prevention Institute
ECNP	European College of Neuropsychopharmacology
eCRF	Electronic Case Report Form
EFAs	Essential fatty acids
EPA	Eicosapentaenoic acid
EPS	Extrapyramidal-motorische Störung
ES	Effect Size
FDA	Food and Drug Administration (USA)
FFQ	Food Frequency Questionnaire
fMRI	Functional Magnetic Resonance Imaging
GC	Gas Chromatography
GCP	Good Clinical Practice
HETE	Hydroxyeicosatetraenoic Acid
HFG	Humanforschungsgesetz
HFV	Verordnung über die Humanforschung mit Ausnahme der klinischen Versuche
HoNOSCA	Health of the Nation Outcome Scales for Children and Adolescents
HPA	Hypothalamic-pituitary-adrenal

hsCRP	High-sensitivity C-reactive Protein
ICD-10	International Classification of Diseases- 10th edition
ICH	International Council on Harmonization
ICH-GCP	International Conference of Harmonisation- Good Clinical Practice
IDMC	Independent Data Monitoring Committee
IEPA	Early Intervention in Mental Health
IES-27-J&E	Jugend- & Elternfragebogen über impulsives Verhalten und Erleben
IFN	Interferon
IICT	Investigator Initiated Clinical Trials
IL	Interleukin
IMP	Investigational Medicinal Product
IQ	Intelligence Quotient
ITT	Intention to Treat
KAZ	Kantonsapotheke Zurich
KJPP	Klinik für Kinder- und Jugendpsychiatrie und Psychotherapie Zürich
KlinV	Verordnung über klinische Versuche in der Humanforschung
K-SADS-PL	Kiddie-Schedule for Affective Disorders and Schizophrenia-Present & Lifetime
LA	Linoleic acid
LC-MS	Liquid chromatography-mass spectrometry
LC-PUFAs	Long-chain polyunsaturated fatty acids
MARS	Medication Adherence Rating Scale
MARS-D	Medication Adherence Reporting Scale-Deutsch
MAQ	Medication Adherence Questionnaire
MCP-1	Monocyte Chemoattractant Protein-1
MCT	Medium Chain Triglycerides
MDD	Major Depressive Disorder
MedDRA	Medical Dictionary for Regulatory Activities
MS	Mass Spectrometry
n-3 FFQ	Omega-3 Food Frequency Questionnaire
OCD	Obsessive Compulsive Disorder

PI	Principal Investigator
pMDD	paediatric Major Depressive Disorder
PMS	Premenstrual Syndrome
PRN	Pro Re Nata (as needed)
PUFAs	Polyunsaturated Fatty Acids
RA	Responsible Applicant
Rbc	Red blood cell membranes
RCTs	Randomized Controlled Trials
RIAS	Reynolds Intellectual Assessment Scales
RR	Relative Risk
RWFT	Regensburger Wortflüssigkeits-Test
SAE	Serious Adverse Event
SD	Standard Deviation
SDQ	Strength and Difficulty Questionnaire
SG	St. Gallen
SIQ-Jr	Suicide Ideation Questionnaire-Junior
SMD	Standard Mean Difference
SNSF	Swiss national science foundation
SOP	Standard Operating Procedure
SSRI	Selective Serotonin Reuptake Inhibitor
SUSAR	Suspected Unexpected Serious Adverse Reaction
TADS	Treatment for Adolescents with Depression Study
TARMED	Tarif Médical
TG	Thurgau
TNF	Tumor Necrosis Factor
TSH	Thyroid Stimulating Hormone
UHR	Ultra High Risk
UK	United Kingdom
USZ	Universitätsspital Zürich

VMLT	Verbaler Lern- und Merkfähigkeitstest
WH	Working Hypothesis
WHO	World Health Organization
WI	Working Instruction
WISC IV	Wechsler Intelligence Scale for Children Version IV
WM	White Matter
ZH	Zürich

University of
Zurich UZH

STUDY SCHEDULE

Study visit	Time (min)	Examiner	-1	Screening/ And Lead in Phase	1	2	3	4	5	
Weeks			7 to 14 days prior baseline	0	6 +/-3d	12 +/-3d	24 +/-5d	36 +/-5d		Drop-out
Study information	15	RC	x							
Informed consent	5	RSP	x							
Inclusion / exclusion	5	R	x		x					
Sociodemographic data	1	R	x							
Medical incl. psychiatric history	1	R	x							
Family history	1	RSP	x							
Physical Health (incl. Tanner)	1	R		x						x
Current medication use	1	R		x	x	x	x	x	x	x
Omega-3 Food questionnaire	5	S		x		x		x	x	x
WHO Assist 3.0 Drug Use	10	R		x		x		x	x	x
Childhood Trauma & Olweus victimization scale	5	S		x						
Intervention			Pla (7-10 d)	Active/Placebo						
Main outcome variables										
Children's Depression Rating Scale CDRS-R	15	R	x		x	x	x	x	x	x
Diagnostic interview (K-SADS-PL)	60	R	x		x*	x*	x*	x*	x	x
Clinician rated variables (at each clinical visit) +/- 2 weeks										
Clinical Global impression Scale CGI-S/I	1	C		x	x	x	x	x	x	x
Children Global Assessment Scale CGAS	1	C		x	x	x	x	x	x	x
Attrition check list inkl. HoNOSCA	8	C		x	x	x	x	x	x	x
Self-report variables (self rating for 13-<18yr, parent rating for 8-13yr)										
Children's Depression Inventory DIKJ	15	S		x	x	x	x	x	x	x
Beck Hopelessness Scale II BHS	5	S		x	x	x	x	x	x	x
Beck Anxiety inventory BAI II	5	S		x	x	x	x	x	x	x
Suicidal ideation questionnaire SIQ-Jr	5	S		x	x	x	x	x	x	x
The Insomnia Severity Index	1	S		x	x	x	x	x	x	x
Perceived Stress Scale PSS-10	5	S		x		x		x		x
Connor-Davidson Resilience Scale	10	S		x	x	x	x	x	x	x
KIDscreen-CAT-27	15	SP	x(P)	x		x		x		x
SDQ	5	SP	x(P)	x		x		x		x
IES-27-J	15	SP	x(P)	x		x		x		x
ASEC (AD side effect self report scale)	5	S		x	x	x	x	x	x	x
Cognitive outcome variables										
BRIEF (executive Functioning questionnaire)	10	SP	x(S,P)			x		x		
Cognitive battery	50	R	x			x		x		
RIAS (short IQ test for matching)	20	R			x					x
Biological outcome variables										
Clinical bloods, hsCRP (2-3d prior randomization)	5	N	x					x		x
Red blood cells (PUFAs), Serum (e.g. immune multiplex marker chip), Buffy coat for tissue repository (e.g. genetic, epigenetic markers)		N	x			x		x		x
Urine (drug screen, F2 isoprostane)	5	N	x			x		x		x
Saliva cortisol	1	N	x			x		x		x
Hair	1	R			x			x		
Other measures										
Drug dispensing/ Pill count/appointment	1	R	x	x	x	x	x	x		
AE				x	x	x	x	x	x	x
MARS-D	3	S		x	x	x	x	x	x	
Approx. time requirement for patient / family only (min)			180	90	90	90	210	120	210	200
* Only subscale 'depressive disorders' will be performed										
R = researcher; C = clinician; S = self-rated; P = parent-rated; N = study nurse										

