- To avoid a selection bias, we decided to allow the use of SSRIs as clinically required. Elsewise, we would probably not be able to include a representative sample of moderately or severely ill children meeting criteria for major depressive disorders. However, the latter may result in an unequal distribution of antidepressant use between the treatment arm and increase the response rate across both treatment arms, making it less likely to address the primary aim of the study. To address this flaw of the study design, we decided to include a further a priori defined analysis approach: We will analyse the primary outcomes using “start of an antidepressant medication” as a “drop out criteria” and jointly model the longitudinal CDRS-R score and the time to study drop out. This will allow us to investigate if omega-3 fatty acids as a sole treatment have antidepressant activity or not. As interim analyses showed that about 20 of our patients started antidepressant treatment within the first 6 weeks (prior to the first follow-up assessment), we will recruit up to 20 additional patients to gain more power for our secondary analyses.

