9.2.2 Assessment of Secondary Outcomes

9.2.2.1 Clinician-Rated secondary outcome measures

- The Clinical Global Impression rating scales CGI [221] is three-item observer-rated scale to measure symptom severity, global improvement/ change and therapeutic response. The Clinical Global Impression – Severity scale (CGI-S) is a 7-point scale that requires the clinician to rate the overall severity. The Clinical Global Impression (CGI-I) is a 7 point scale that requires the clinician to assess how much the patient's illness has improved or worsened relative to a baseline state (1, very much improved; 2, much improved; 3, minimally improved; 4, no change; 5, minimally worse; 6, much worse; or 7, very much worse). The Impression – Efficacy Index is a 4x4 point index that results out of the therapeutic effect versus side effects.

- The Children's Global Assessment of Functioning CGAS [222] is a numeric scale (1 through 100) used by mental health clinicians to rate the general functioning of children under the age of 18.
- The Health of the Nation Outcome Scales for Children and Adolescents – HoNOSCA [223] is a mandatory quality and outcome measure for clinicians working in child- and adolescent psychiatric services in Switzerland (many other countries have also implemented this short and comprehensive outcome scale for service evaluation). The HoNOSCA scores the behaviour, impairments, symptoms and social functioning of children and teenagers with mental health problems using 13 global items. The severity of each problem is scored on a scale of 0-4. Clinician will rate the HoNOSCA together with the CGI and CGAS and the attrition checklist requiring about 10 minutes.

All three scales will be administered at baseline and at each clinical visit. Given that these assessments depend on the clinicians' appointments with the patients, the time frame for these particular scales is extended to \pm 2 weeks.

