9.3.7 Clinical Care and monitoring of clinical visits

Usually clinicians will see outpatients on a weekly basis for the first six weeks, and gradually increase the time lap between visits (e.g. on a two weekly bases between week 6-12), and thereafter as clinically indicated. However, clinicians are allowed to see patients whenever clinically indicated. Clinicians will perform clinician-based assessments (CGI, CGAS, and HoNOSCA) and complete the attrition checklist that includes the documentation of service use and adverse events at any clinical visit.

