5.1 Primary endpoints

- CDRS-R total score trajectories from baseline to week 36 (measured at baseline, 6, 12, 24, and 36 weeks)

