7.1 Primary endpoint

- CDRS-R total score from baseline (post-placebo-lead-in) to week 36

The primary analysis consists of a joint model linking (1) a linear mixed effects model for CDRS-R total score over time with (2) a Cox proportional hazards model for the risk of the event new initiation of or increase in antidepressant use (intervention dropout) and (3) a Cox proportional hazards model for the risk of study dropout as a competing event. This assumes that whether a participant has missing data and at what time this occurs contains additional information that should be taken into account and corresponds to an MNAR missing data mechanism.

Participants are censored at whichever occurs first of: antidepressant initiation/increase, loss to follow up, consent withdrawal, and study exit due to non-adherence. Participants lost to follow up, withdrawing consent, and exiting the study (as per protocol) due to non-adherence are considered alike and these events considered one event type: study dropout.

The linear mixed effects model for the longitudinal CDRS-R total score outcome $Y_i(t)$ measured at time t for participant i takes the following form:

$$\begin{aligned}
 Y_i(t) &= m_i(t) + \varepsilon_i(t), \\
 m_i(t) &= \beta_0 + \beta_1 \text{intervention}_i + \beta_2 t_{base} + \beta_3 t_{6weeks} + \beta_4 t_{12weeks} + \beta_5 t_{24weeks} + \beta_6 t_{36weeks} \\
 &\quad + \beta_7 t_{base} * \text{intervention}_i + \beta_8 t_{6weeks} * \text{intervention}_i + \beta_9 t_{12weeks} * \text{intervention}_i \\
 &\quad + \beta_{10} t_{24weeks} * \text{intervention}_i + \beta_{11} t_{36weeks} * \text{intervention}_i \\
 &\quad + \beta_{12} \text{age}_i + \beta_{13} \text{gender}_i + \beta_{14} \text{hsCRP}_i \\
 &\quad + \beta_{15} \text{antidepressant} + \beta_{16} \text{omega-3 index} \\
 &\quad + b_{i0} + b_{i1}t + b_{s0},
 \end{aligned}$$

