4. **Delta-based multiple imputation for MNAR analysis:** The data after intervention dropout or study dropout is considered to be missing. Multiple imputation under MAR will be performed separately within each treatment arm (White et al 2011) using imputation models containing the minimization factors, baseline antidepressant use and omega-3 index. It will be assumed that participants initiating/increasing non-randomized antidepressant use would have had worse outcomes than observed had they not used the non-randomized antidepressant. A range of mean differences δ from a 25% increase in CDRS-R score (25% worse outcome) to a 100% increase (by 25% increments) in the CDRS-R score in the intervention dropouts as compared to the observed cases will be considered. Delta will then be added to the imputed

CDRS-R scores for the participants with intervention dropout. Results will be combined using Rubin's rule. This is repeated for each delta.

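### For the roughly 20 patients who start an antidepressant before week 6, the SAP's imputations use no measured post-baseline severity, although CGI-S and CGAS are planned at each clinical visit

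*Protocol*

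**What the plan says.** **Clinician ratings.** The Study Schedule heads these scales "Clinician rated variables (at each clinical visit) +/- 2 weeks". Protocol 9.2.2.1 adds: "All three scales will be administered at baseline and at each clinical visit". Protocol 9.3.7 repeats it: "Clinicians will perform clinician-based assessments (CGI, CGAS, and HoNOSCA) and complete the attrition checklist". On frequency, it says that usually "clinicians will see outpatients on a weekly basis for the first six weeks".

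**Research ratings.** SAP 5.1 defines the primary endpoint as "CDRS-R total score trajectories from baseline to week 36 (measured at baseline, 6, 12, 24, and 36 weeks". No CDRS-R falls between baseline and week 6.

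**Early starters.** Protocol 6.3.2 reports that "about 20 of our patients started antidepressant treatment within the first 6 weeks (prior to the first follow-up assessment". Protocol 8.7.1 and 8.7.2 leave the decision to start to the treating side, independently of the research team.

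**Analysis.** In the primary joint model, SAP 7.1 states: "Participants are censored at whichever occurs first of: antidepressant initiation/increase". The delta-based imputation (SAP 7.1.2 item 4) is done within arm, "using imputation models containing the minimization factors, baseline antidepressant use and omega-3 index". SAP 7.2.1 lists the same predictors for remission and response, and adds the baseline score for DIKJ and KIDscreen. CGI, CGAS and HoNOSCA appear nowhere in the SAP.

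**The concern.** SAP 7.1.2 item 3 says that antidepressant use is not random across participants but related to intermediate outcomes and possibly to arm. For a patient who starts before week 6, the only recorded intermediate outcomes under the schedule are the treating clinicians' ratings. If these are left out, a patient who was worsening is imputed as average for his or her baseline. No-antidepressant severity in starters is then likely to be understated.

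SAP section 1 expects more antidepressant use in the control arm, so the error would be larger there and would shrink the treatment contrast. MAR imputation is the main analysis for remission, response, DIKJ and KIDscreen. Response is judged within 12 weeks, so for an early starter both assessments that could show response (weeks 6 and 12) are imputed. Adding earlier CDRS-R visits to the imputation model cannot help these patients, because they have none.

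**Working it through.** **1. What each SAP analysis knows about an early starter**
- Primary joint model (7.1): baseline CDRS-R plus the start time, which acts through the association term α·m(t).
- Sensitivity 1, typical ITT: CDRS-R from week 6 on, as observed on the antidepressant. Starting one is not a withdrawal criterion (Protocol 8.7.2).
- Sensitivity 2, modified ITT: baseline only.
- Sensitivity 3, per protocol: patient excluded.
- Sensitivity 4, delta-based imputation: baseline only, then shifted.
- Remission, response, DIKJ, KIDscreen (7.2.1): baseline only, imputed under MAR.

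**2. Share affected.** The figure of about 20 is an observed count, so there is no formula to reproduce. Protocol 6.2 gives 225 randomised, 20 more needed, and up to 20 further: 20/225 = 8.9%, 20/245 = 8.2%, 20/265 = 7.5%. At the anticipated 30% use, 0.30 × 220 = 66 starters, of whom 20 are about 30%.

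**3. Early starters alone (illustration).** Assume 225 patients split equally (112.5 per arm), with early starters *d* SD worse at week 6 than baseline predicts. Missed contrast = (difference in early starters between arms)/112.5 × *d*.
- 10 vs 10: 0.
- 5 vs 15: 10/112.5 × 0.5 = 0.04 SD for *d* = 0.5, and 0.089 SD for *d* = 1.
- 2 vs 18, *d* = 1: 16/112.5 = 0.14 SD.

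If a rating with partial correlation *r* recovers a fraction *r*², the 0.089 becomes 0.089 × (1 − 0.09) = 0.081 at *r* = 0.3, or 0.089 × (1 − 0.49) = 0.045 at *r* = 0.7.

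**4. All starters (simulation, assumed inputs).** Main set-up: 120 per arm, 400 runs. Severity has a random intercept, a random slope and an autocorrelated part (8-week correlation time), each SD 7. CDRS-R error SD is 4. Rating = severity/10 plus noise of SD 0.6. The weekly start hazard is exponential in the rating. The true no-antidepressant week-36 difference is about −4.5. Imputation is by arm and already uses all earlier CDRS-R visits, which is more than the SAP lists.

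| Starts, placebo vs omega-3 | Bias without ratings | Bias with pre-start ratings |
|---|---|---|
| 38% vs 23% | 0.6 | 0.3 |
| 38% vs 23%, coded separately | 0.66 | 0.21 |
| 32% vs 29% | 0.2 | 0.1 |
| 33% vs 30%, coded separately | 0.25 | 0.14 |
| about 35% vs 14% | 0.6 | 0.3 |
| noisy rating | 0.59 | 0.56 |

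Positive bias is towards the null. In the second row, placebo response was put at 35.7% without ratings and 33.6% with them (true 33.0%). The SD of the estimate rose by 2% to 6%. In a variant that treated the last pre-start rating as if taken at the next study visit, placebo-mean bias overshot from −1.9 to +0.9, and contrast bias went from 0.77 to −0.22.

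**5. Delta-shifted results.** The smallest planned delta is 25%. With an assumed week-36 mean of 28 to 45, that is 7 to 11.25 points per starter.
- 38% vs 23%: 0.15 × 7 to 11.25 = 1.1 to 1.7 points away from the null, against a bias of 0.6.
- 32% vs 29%: 0.03 × 7 to 11.25 = 0.2 to 0.3, against 0.2.

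**6. Bias against precision.** The simulation's variance is 3 × 49 + 16 = 163 (slope SD read as per 36 weeks), so the complete-data SE is √(163 × 2/120) = 1.65 and its square 2.72.
- 32% vs 29%: mean squared error 2.72 + 0.2² = 2.76 without ratings. With ratings it is 2.84 (SE +2%) to 3.01 (SE +5%).
- 38% vs 23%: 2.72 + 0.6² = 3.08 without. With ratings it is 2.92 (+2%) to 3.09 (+5%).

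**The case against.** A reader might infer four stronger things from the SAP's silence on these ratings. The documents do not support them.
- *No analysis has any post-baseline severity for early starters.* Sensitivity 1 uses their later CDRS-R, and sensitivity 3 drops them.
- *The early leavers also have a baseline score only.* Protocol 6.2 reports 21 drop-outs before the first follow-up, but Protocol 8.5 plans a drop-out visit that includes CDRS-R. It is only attempted, and the SAP does not say how it is used.
- *The delta-based results are also pulled towards the null.* Item 4 shifts starters upwards because they are assumed to be worse. By step 5, the smallest delta already offsets a bias of this size.
- *The primary joint model is at fault.* It uses the start time and declares an MNAR mechanism. For early starters that information rests on the model and not on a measured score, but it is not ignored.

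Three further objections stand in part. First, the ratings may not exist where they are needed. The schedule marks them in study-visit columns with a two-week window, weekly visits are only usual and only for outpatients, and no inpatient frequency is given. Second, the simulation is favourable: its rating correlates about 0.79 (baseline) to 0.85 (week 36) with CDRS-R, and 9% to 18% start before week 6 against about 8.9% in the trial. Its gain covers all starters, not only the early ones. When starts are nearly balanced, the lost precision outweighs the bias removed (step 6). Third, the no-antidepressant mean is not the primary estimand of SAP 4.1. It is, however, what the secondary analyses target when they set data after a start to missing.

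**Conclusion.** The point holds for the modified ITT and the imputation-based analyses. There, the roughly 20 early starters contribute no measured post-baseline severity, and MAR given baseline variables alone sits badly with the SAP's own statement about why antidepressants are started. The practical weight falls on remission, response, DIKJ and KIDscreen, where MAR imputation is the main analysis.

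The likely effect is a modest bias towards the null, about 0.2 to 0.7 CDRS-R points at week 36 across the main scenarios. This rests on more starts on placebo, on starts driven by current severity, and on the variance components listed above. It covers starters at any time, so the early starters account for only part of it. DIKJ and KIDscreen were not simulated. How much the ratings recover depends on their correlation with CDRS-R: about half or more when it is high, almost nothing when it is low. The direction for the delta-shifted results is not established, and nothing here calls for a change to the primary joint model.

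**What to change.** In SAP 7.1.2 item 4 and SAP 7.2.1:
- Add CGI-S and CGAS recorded before antidepressant start or study exit as auxiliary variables in the arm-specific imputation models.
- Enter each rating with its date and match it to ratings from the same period in continuing patients. Do not slot it into the next study visit, which can overcorrect the arm means.
- Set ratings made after an antidepressant start to missing.
- For early leavers, use any CDRS-R from the drop-out visit.
- Report how many early starters have a pre-start rating.
- Leave the primary joint model unchanged.

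The cost is SAP wording plus linkage of data already scheduled for capture; no new assessment is needed. The downsides are irregular or missing ratings, a standard error about 5% larger (2% to 6% in the simulations), and little gain if the ratings track CDRS-R poorly.
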